4.2.2 Post-Screening Study Visits

Baseline hdEEG Sleep Recording (Visit 2)

Participants will come to the Wisconsin Sleep laboratory (accredited by the American Academy of Sleep Medicine) for their first hdEEG night approximately 1 to 2 hours before their usual bedtime. During this visit, waking and sleep hdEEG (256 channels) recordings will be acquired using an Electrical Geodesics NetAmps 300 System. The hdEEG and PSG systems (i.e., Geodesics System and Alice 5 System) have 510(k) clearance and are being used in accordance with the indications in their labeling. Prior to sleep, spontaneous eyes open and eyes closed EEG (2-4 sessions > 2 minutes long), along with peripherally evoked potentials (auditory, 50 ms 2000 Hz pure tones; visual, checkboard; somatosensory, electrical stimulation of the median nerve 10% above threshold), measures of arousal (computerized infrared pupillography (DP2000 Human Laboratory Pupillometer, Neuroptics, Inc., Irvine, CA) and flicker fusion rate (Flicker fusion analyzer, Lafayette Inc., Loughborough, UK)), and/or several short vigilance tasks (the Psychomotor Vigilance Test ; PVT or brief version, PVT-B (Basner, Mollicone, & Dinges, 2011), the Sustained Attention to Response Task (SART) (Van Schie et al., 2012), the Compensatory Tracking Task (CTT) (Huber et al., 2013), and/or the Divided Attention Driving Task (DADT) (Sunwoo et al., 2012) may be collected 1 hr prior to the subject's usual bedtime. Participants will also complete some questionnaire measures prior to bedtime, including measures of arousal and mood (i.e., DASS, Visual Analogue Scale (VAS) and State-Trait Anxiety Inventory (STAI)). The sleep hdEEG will be integrated with clinical polysomnography (PSG) using the Alice 5 Sleepware system to further rule out common sleep problems such as periodic leg movements (PLMs). Sensors to be included for the clinical PSG will be: EOG, chin and leg EMG, EKG, and SpO₂; optional PSG sensors may be included depending on the subject comfort or if the ApneaLink results were inconclusive, including nasal cannula, thermistor, respiration belts, a snore microphone, and a position sensor. The entire setup for this recording takes approximately 45-60 minutes. Audio and low-resolution video using an infrared camera will also be recorded during the sleep nights to assist with sleep scoring of the EEG and to allow real-time monitoring of subjects. In addition to providing important information for assessing sleep, audio/video monitoring provides additional subject safety by allowing contact with the subject at all times. After the completion of the study, these recordings will be erased. Participants will be excluded if they evidence a periodic limb movement arousal index >10. Oximetry data will be evaluated by the physician and any subjects who shows evidence of sleep apnea (ODI >5) or hypoxemia (oxyhemoglobin saturation <89% for more than 5 min) will be excluded; this is unlikely after baseline screening. Participants will also complete some questionnaire measures upon awakening, including measures of arousal and mood (e.g., GCTI, PSAS, VAS, STAI, Post-Sleep Questionnaire) in addition to waking EEG, evoked potential recordings, and the brief attention tasks, time permitting.

Serial Awakening hdEEG Sleep Recording (Visit 3)

Visit 3 will be scheduled for the following night, unless scheduling does not permit. In the event that the participant is unable to return the following night, Visit 3 will be scheduled for within two weeks of Visit 2 and participants will wear actigraphy during that time. For participants completing Visit 3 the following night, they will spend the next day in their usual activities but will be instructed not to sleep; they will wear actigraphy to verify that they were not sleeping or resting during the day. They will return that night approximately 1 to 2 hours before their usual bedtime to complete a second hdEEG study (Visit 3). During this visit they

Insomnia and Sleep Patterns Study

may repeat the waking EEG, evoked potential recordings, arousal measures, and attention tasks. They will also complete some questionnaires prior to bedtime (i.e., VAS and STAI). Additional PSG channels (including EOG, EMG, EKG, and optional PSG sensors if warranted) will be applied prior to lights out to assist in accurate sleep staging. All participants will then complete the serial awakening night in which participants are periodically probed with auditory stimuli during the night. After the onset of sleep, participants will be awakened repeatedly using 10 sec tones starting at 40dB and increasing by 5 dB every 30 sec until a full awakening is achieved. This procedure has been used effectively to estimate the effects that background alpha and sleep spindle activity have on sleep stability (Dang-Vu et al 2010, McKinney et al 2011). After indicating that they have heard the tone, subjects will confirm that they are awake by answering two questions “What was the last thing going through your mind after hearing the sound” and “were you awake or asleep”. Participants will then be encouraged to fall back asleep. We will aim to evoke at least 1-2 awakenings in each stage (N1, N2, N3, REM) for the first 3 sleep cycles so as to have a minimum of 12 total awakenings. The timing of these awakenings will be approximated based on the sleep architecture of the baseline night. Sleep recordings will end when the participant awakens in the morning, or if they cannot return to sleep during the night. No awakenings will be attempted after the subject’s normal waking time and they will be allowed to sleep *ad libitum* after this time if they wish. Participants will also complete some questionnaire measures upon awakening, including measures of arousal and mood (e.g., GCTI, PSAS, VAS, STAI, Post-Sleep Questionnaire), as well as waking EEG, evoked potential recordings, and the brief attention tasks if time permits. As before, participants will be under constant staff supervision during the recording. If participants are unable to sleep longer but do not feel rested, we will provide transportation back home.

Follow-up hdEEG Sleep Recording (Visit 4)

Visit 4 is an optional study visit for all subjects. This third hdEEG study will occur at least 1 but not more than 4 weeks after Visit 3. Pre-recording activities and setup will be exactly as in the Visit 3 recording except no auditory tones will be played during the night and participants will complete the DASS prior to bedtime. This recording will be used to establish the stability of baseline sleep recordings. Likely all insomnia participants will be invited to this visit. At least 10 healthy sleepers will be invited as stability of recordings is less of a concern, though collecting a sub-sample will help to confirm stability nonetheless. Participants with depression and insomnia will be invited if their participation is deemed clinically appropriate by study clinicians (e.g., if a participant is not on a psychotropic medication that will interfere with recordings at baseline, but has desire to start a psychotropic medication for depression that would interfere with recordings in the near future, we would not invite this participant so that his/her study participation time is kept to minimal time and depression treatment can commence).

Repetition of Visits 2 and 3 in Insomnia Patients on Sleep Medication (Visits 5 and 6)

Visits 5 and 6 are optional for participants with insomnia, either with or without depression. Some participants in the study may choose to return to or initiate treatment for insomnia with a sleep medication under the supervision of their personal doctor. Participants who choose to begin a sleep medication following completion of Visits 2 and 3 (and 4, if they opt to complete this optional visit) will be invited to return to the laboratory to repeat Visit 2 (as Visit 5) and Visit 3 (as Visit 6) procedures. Visits 5 and 6 will follow exactly the procedures outlined in Visits 2 and 3, respectively.

Insomnia and Sleep Patterns Study

Visits 5 and 6 will be scheduled for at least 1 week after participants start a sleep medication.

For Visit 2, 3, 4, 5, or 6, if technical problems arise during completion of the protocol (e.g., mechanical issues, mistakes with administration of the protocol), study staff may ask participants to complete that visit again. If the participant agrees, the visit will be rescheduled at the participant's convenience. They will be paid again for the visit.

Table 1

Table 1 specifies the assessments and questionnaires that may be completed at each of the study time points.

Assessment or Questionnaire	Study Visit					
	Phone Screening	Baseline Screening (Visit 1)	At-Home Sleep Study	Baseline Sleep Recording (Visits 2 and 5)	Serial Awakening Sleep Recording (Visits 3 and 6)	Follow-Up Sleep Recording (Visit 4)
Phone screening	X					
Demographics		X				
Height and weight		X				
Pregnancy/Menstrual Cycle		X				
ISI		X				
Handedness		X				
SCID		X				
MMSE		X				
Medical history		X				
RDC Criteria		X				
HRSD		X				
PSAS		X		X	X	X
GCTI		X		X	X	X
DBAS		X				
DASS		X		X		X
PSWQ		X				
Penn CNP		X				
VAS				X	X	X
STAI				X	X	X
ApneaLink			X			
Actigraphy			X			
Sleep logs			X			
Pupillometry				X	X	X
Flicker Fusion Rate				X	X	X

PSG/EEG	X	X	X
Post-Sleep Questionnaire	X	X	X

4.3 Data Safety and Monitoring Plan

In this study, as in similar studies, there is no formalized Data Safety Monitoring Board (DSMB). However, serious adverse events and unanticipated problems would be reported to the IRB in accordance with posted IRB guidance (<http://kb.wisc.edu/images/group78/18324/ReportingTimeframesJanuary2013.pdf>).

In addition, there will be a formal process for review and monitoring of study-related adverse events. All adverse events are evaluated at each visit by study staff and if any arise, will be reported to the principal investigator within 24 hours – or immediately depending on severity. The principal investigator and main co-investigators will review cumulative data on adverse events at least every 3 months. If any changes in protocol or procedure are warranted by this review, they will be filed with the IRB, and the affected study visits will not continue until changes are approved. If any pattern of adverse events occurs, the principal investigator and main co-investigators will form an ad hoc panel including other investigators at UW to review the events and determine the appropriate course of action. Outside consultation will be obtained if the situation requires.

Furthermore, all study team members will be trained on the IRB-approved protocol. We will meet at least monthly to discuss study progress, which will include a review of any changes to the IRB-approved protocol, as needed. In addition, all study team members will immediately be alerted to changes in the protocol via email or in person discussions. We will conduct regular (i.e., at least monthly) internal audits of all study materials (e.g., completed participant materials, blank study forms, study protocols) to assure that the proper, IRB-approved forms are being used and that there are no deviations from the IRB-approved protocol.

4.4 Statistical Considerations

4.4.1 Sample Size Justification

The strength of this study design is that it will allow us to characterize the cortical activity of insomnia patients with a unique combination of temporal and spatial resolution during sleep initiation, normal sleep, and awakening from sleep. As such, a number of the questions that can be addressed with this design are highly novel for which there is little direct evidence on which to base sample size calculations. However, the substantial pilot data collected from a population of insomnia patients as well as age- and sex- matched controls for one of the primary hypotheses (2.7.2a) allows us to confidently support our proposed choice of sample size. The Cohen's *d* effect size averaged across the significant source cluster was 1.15. Our power to detect an effect of this magnitude in our proposed final sample size of 20 per group using an alpha level of *p*=.05, 2-tailed would be approximately 94%. Our power to detect the difference between potential subgroups of sleep maintenance versus sleep onset with the insomnia group alone (10 per group) would be approximately 68%. Furthermore, on the basis of other similar analyses with relatively small sample sizes (e.g. - <20 subjects per group) examining local sleep homeostasis (Huber et al 2004), the traveling phenomena of slow waves (Massimini et al 2004),

the cortical localization of evoked K-complex slow waves (Riedner et al 2011), slow wave reduction in hypersomnolent depressives (Plante et al 2012b), sleep spindle reductions in schizophrenia (Ferrarelli et al 2007, Ferrarelli et al 2010), the current study design should provide us with adequate statistical power.

4.4.2 Proposed Data Analytic Strategy

[name] [name] (PI), [name], and [name] will be responsible for performing and overseeing data collection and analysis. Statistical analysis will be planned and executed in conjunction with UW BARD (<https://ictr.wisc.edu/Biostatistics>). Although our preliminary work has allowed us to identify several primary objectives, described below, with clearly identified primary outcome measures and *a priori* analysis plans, the protocol is also largely designed to be exploratory in nature. Therefore, it is likely that several promising analysis paths will emerge once the data have been collected that cannot be formally identified in advance, but that are in keeping with the primary and secondary objectives of the study. Such additional exploratory analyses naturally raise the issue of multiple comparisons. Our laboratory has been a leader in designing and implementing the use of hdEEG in sleep, particularly in clinical populations, and has been successful in funding and publishing this type of exploratory research. Where appropriate, established procedures will be used to evaluate a family of related questions (e.g., ANOVA for comparison between groups across frequency bands) with reasonably chosen post-hoc corrections for multiple comparisons (e.g., Bonferroni). However, in all cases these procedures will be adapted to account for the most pervasive multiple comparison problem in hdEEG and other neuroimaging (independent tests between hundreds of electrodes or thousands of potential cortical sources) using statistical nonparametric mapping techniques (SnPM) as described below.

Normal hdEEG sleep imaging (Primary Objective 1)

Sleep stages will be visually scored for 30-s epochs according to standard criteria (AASM). The study Principle Investigator, [name], a board-certified sleep specialist with over 25 years of scoring experience and the medical director of the Wisconsin Sleep laboratory, will supervise the scoring and review all studies for the presence of any clinical sleep disorders. Data preprocessing and analysis of sleep data will be performed using NetStation (EGI) as well as custom made software using Matlab (Mathworks) and EEGLab packages. Power spectra of consecutive 6-s epochs (FFT routine, Welch's averaged modified periodogram with Hamming window) will be computed for all derivations in order aid in identification of artifacts and for initial scalp exploration. Only epochs without artifacts will be used for further analysis. Given the frequency of muscle and eye movements, additional REM artifacts will be removed using scalp-level temporal independent component analysis (ICA). Data will be analyzed both in the time (e.g. slow wave and spindle waveform detection) and frequency domains. As stated above, one of the primary study objectives is to examine differences in the cortical sources of sleep waveforms in insomnia patients with and without depression compared to healthy sleeping controls during normal sleep. The initial step of the planned analysis will be to explore the scalp level EEG sleep power topographies of different frequency bands (Delta, Theta, Alpha, Sigma, Beta, Gamma) across the groups and across sleep stages (N1, N2, N3, REM) throughout the entire night in order to identify reasonable temporal window(s) for further analysis as computational demands of cortical source imaging require that the data to be analyzed is on the

Insomnia and Sleep Patterns Study

order of minutes instead of hours. Preliminary results suggest that tonic alpha power during N3 sleep may distinguish between these groups, but it is also conceivable that events like slow waves or spindles may provide additional distinguishing information, and windows around these events may be relevant. The **outcome measure** addressing **this first primary study objective** will be the cortical localization maps of band-pass filtered EEG data in the frequency range of interest (identified by the scalp-level analysis from the initial steps, e.g. alpha) using a distributed inverse solution (i.e. LORETA, for details of the methods involved see (Murphy et al 2011)). All group comparisons of distributed source localization maps will be analyzed using statistical nonparametric mapping (SnPM)(Nichols & Holmes 2002) which is ideally suited to address the multiple comparison issues inherent to neuroimaging and which does not make unwarranted assumptions about data distribution. This method has been successfully applied in a number of hdEEG studies in our laboratory (Ferrarelli et al 2007, Huber et al 2006, Huber et al 2004), and compares favorably with Statistical Parametric Mapping for analyses having low degrees of freedom.

Falling asleep imaging (Primary Objective 2a)

During both the baseline and serial awakening sleep nights, the descent into (or back into) sleep will be analyzed by dividing the interval between the last appearance of occipital alpha and the first instance of a burst of slow waves (more than 2 slow waves consecutively without an arousal) into 10 equally spaced temporal bins prior to cortical source estimation. Distributed source localization maps for individual frequency ranges will then be average within subject and then within group prior to statistical analysis.

Sleep arousal imaging (Primary Objective 2b)

During both the baseline and serial awakening sleep nights, spontaneous arousals/awakenings will also be explored using similar methods to the falling asleep analysis except the windows of interest will be fixed at 12 seconds (10 intervals = 2 minutes) given that there is no *a priori* criteria for establishing the arousal onset. Additionally, for the serial awakening sleep nights, stimulus evoked responses during sleep will be examined using similar methods as described above, both in time (evoked potential analysis) and time-frequency (event related spectral perturbation) as we have done previously (Landsness et al 2009, Riedner et al 2011) except the analysis window will be temporally fixed around the stimulus trigger (15 sec window, including 2 seconds before and 3 seconds after 10 second auditory stimulus onset and offset, respectively). Arousals will be scored according to established arousal criteria (Bonnet et al 2007). Stimuli will be categorized into those that did not cause an arousal, those that did cause an arousal, and those that resulted in a full awakening. The **outcome measures** addressing the second primary objective will be similar to the outcome measure for the first primary objective, cortical localization maps of band-pass filtered EEG data, except that the temporal windows of interest will be predefined as described above. Further exploratory analyses will employ Cox regression (see McKinney et al) to investigate the ability of alpha in particular cortical regions of interest (defined in the baseline analysis) to predict sleep stability in insomnia patients and controls.

Correlations between EEG abnormalities and behavioral variables

Comparison of behavioral data, as well as traditional sleep architecture variables will be analyzed using established procedures (e.g. ANOVA for repeated measures and post-hoc tests).

Insomnia and Sleep Patterns Study

Correlations with EEG and/or source localization of power will either be examined using a region of interest approach or using SnPM techniques to explore cortical areas whose activity may be related to the variable of interest, depending on the nature of the exploratory analysis.

Waking EEG and Evoked Potentials analysis

EEG data will be analyzed similar to sleep and the presentation of stimuli during sleep except that planned comparisons will be performed between recordings made during the evening before and morning after baseline sleep. Exploratory analyses will also be conducted on this comparison across the serial awakening night to examine the differential effect of sleep disruption.

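### No provision masks sleep and arousal scorers to diagnostic group, although their scoring selects part of the data that enter the primary source maps

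*Combined protocol and SAP*

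**What the plan says.** The relevant text is spread over Sections 4.2.2 and 4.4.2 of the combined protocol and SAP.

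- **Staging.** The rule is "Sleep stages will be visually scored for 30-s epochs according to standard criteria (AASM". The principal investigator "will supervise the scoring and review all studies for the presence of any clinical sleep disorders", and is also listed among those who "will be responsible for performing and overseeing data collection and analysis".
- **Material used for scoring.** Under Visit 2: "Audio and low-resolution video using an infrared camera will also be recorded during the sleep nights to assist with sleep scoring of the EEG".
- **Artifacts.** "Only epochs without artifacts will be used for further analysis". Power spectra help to find artifacts, and independent component analysis removes further ones in REM. The text does not say how much of the rejection is manual.
- **Objective 1.** Scalp power in each frequency band is explored "across the groups and across sleep stages (N1, N2, N3, REM) throughout the entire night in order to identify reasonable temporal window(s) for further analysis". The outcome is the source map in the band picked out by that exploration.
- **Objective 2a.** The falling-asleep interval runs from the last occipital alpha to the first slow-wave burst uninterrupted by an arousal. Who or what marks these points is not stated.
- **Objective 2b.** "Arousals will be scored according to established arousal criteria". Spontaneous arousals are analysed in ten 12-second intervals. Stimuli are sorted into three classes: no arousal, arousal, or full awakening.

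No section says whether the people doing this work know the participant's group. No second scorer or check of scorer agreement is described for sleep scoring.

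**The concern.** The groups are defined by diagnosis before any recording is made, and the hypotheses in Section 3.3 have a direction for alpha and predict abnormal arousal responses in patients. Visual staging involves judgement at the borderline between stages, and arousal scoring may do so too. If the scorer knows the group, expectation can influence which epochs and events are selected, and the selected data are what the source maps compare.

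The planned nonparametric mapping (SnPM) does not protect against this. It controls error over many electrodes or sources, given the data supplied to it; it cannot undo a difference between groups in how those data were chosen.

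The plan takes comparable care elsewhere. Section 4.2.1 allows interviews to be recorded as a check on their validity and reliability, and Section 4.1.3 has a different investigator screen an investigator's own patients. Scoring has no such safeguard.

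**Working it through.** **1. The plan's own figures.** Section 4.4.1 gives d = 1.15, two-sided alpha 0.05, and power of about 94% at 20 per group and about 68% at 10 per group. With a two-sample t-test, the noncentrality is d × √(n/2) on 2n − 2 degrees of freedom.

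- n = 20: 1.15 × √10 = 3.64 on 38 df; power 94.3%.
- n = 10: 1.15 × √5 = 2.57 on 18 df; power 68.2%.

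Both reproduce. This point disputes neither.

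**2. Where scoring enters each primary outcome.**

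| Outcome | Set by scoring | Not set by scoring |
|---|---|---|
| Objective 1 source maps | Which epochs count as N1, N2, N3 or REM when the window is chosen; any manual artifact rejection | Map values, which are computed from the signal |
| Objective 2a falling asleep | The requirement that no arousal interrupts the burst | Whether the alpha and slow-wave marks are manual is not stated |
| Objective 2b spontaneous arousals | Where the windows fall | Their length: 10 × 12 s = 120 s |
| Objective 2b evoked responses | The split between no arousal and arousal | The window, fixed to the stimulus: 2 + 10 + 3 = 15 s; full awakening, where the participant signals hearing the tone and answers two questions (Section 4.2.2, Visit 3) |

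So the route for bias is the selection of epochs, events and categories. It is not a rating of the outcome itself.

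**3. Whether masking is provided for.** The nearest text is Section 4.5.1, where participants are identified by subject number and initials. That protects confidentiality; it does not withhold diagnosis from staff. The same section says that participants are recognizable in the recordings, and Section 4.2.2 uses the video to help scoring.

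**4. What an unknown shift would do.** The document gives no basis for its size, so this is illustration only. Assume that there is no true difference, that selection shifts the group difference by δ SD in either direction, and that one two-sided 5% t-test is done at 20 per group. The noncentrality is δ × √10 on 38 df.

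| Assumed δ | Noncentrality | Rejection rate |
|---|---|---|
| 0 | 0 | 5.0% |
| 0.1 | 0.32 | 6.1% |
| 0.2 | 0.63 | 9.5% |
| 0.3 | 0.95 | 15.2% |
| 0.5 | 1.58 | 33.8% |

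The planned test is SnPM over a map, not a single t-test, so the table shows only how sensitive a comparison of this size is to a modest shift.

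**The case against.** The strongest reply is that the maps are computed from the signal, most Objective 2 windows are predefined, staging follows AASM criteria, part of the artifact handling is algorithmic, files already carry subject numbers, and Section 4.4.2 calls the protocol largely exploratory. Much of this stands, and it rules out four stronger readings that a reader might infer.

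- **That scorers know the group.** The document is silent; it does not say so. Visual scoring is also explicit only for sleep stages. For arousals it is an inference.
- **That scoring sets all the primary windows.** It does not. The evoked window follows the stimulus, and full awakening rests on the participant's response.
- **That bias must favour the hypothesis.** This is not shown. If borderline, aroused-looking epochs were moved out of N3 in patients, the N3 that remained could contain less alpha, which would work against the hypothesis.
- **That the pilot arousal index gives the size.** In Table 1 of Section 2.2 the index does not differ clearly between groups (overall p = .789), it is not a primary outcome, and no link from over-scored arousals to map values is given.

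What the reply does not answer is stage selection in Objective 1, the placement of spontaneous-arousal windows, and the split between no arousal and arousal. Those steps depend on scoring, and nothing in the text keeps group from the scorer. An exploratory aim does not lessen the need for even-handed selection between groups.

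**Conclusion.** The point holds in a limited form. In a comparison of known diagnostic groups, stages are scored visually under the principal investigator's supervision and arousals by published criteria, with no provision for masking. That scoring selects part of the data behind the primary source maps, so knowledge of group could bias them. Neither the direction nor the amount can be established from the document; the rejection rates above rest wholly on assumed shifts.

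The conclusion assumes that some scoring or event marking involves judgement, which is explicit for staging, and that scorers could learn the group, which nothing in the text prevents. If masked scoring is already the laboratory's practice, one sentence saying so would settle the matter. This is a cheap improvement worth making. It does not invalidate the design, and the stated power is unaffected.

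**What to change.** Add to Section 4.4.2 that the research stage scoring, arousal scoring, manual artifact rejection and event marking (including the Objective 2a marks) are done from coded files. Group, clinical and questionnaire data are withheld from scorers until that scoring is locked. Where possible, use existing staff who did not run that participant's visits.

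Keep two activities separate from the locked research scoring, on their existing schedule and without delay:

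- the clinical and eligibility review of recordings, because Visit 2 findings lead to exclusions;
- the look at baseline sleep architecture used to time the Visit 3 awakenings, because Visit 3 is normally the next night.

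Neither has to be masked, provided that it does not feed the locked scoring.

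The cost is a small handling effort: coding files, ordering the work and assigning scorers. Masking will be imperfect where video is used, since participants can be recognized, and on very disturbed nights. The report should say so. The change is best made before scoring starts: Sections 4.2.2 and 4.5.1 have the audio and video erased at the end of the study, after which masked re-scoring from the same material would not be possible.
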